Study Protocol

Official Title:

Comparison of Complication Rates of Onlay vs Sublay Mesh Repair of Incisional Hernia

Brief Title:

Complication Rate of Onlay vs Sublay Mesh Repair in Incisional Hernia

ClinicalTrials.gov Identifier:

NCT ID: Not Yet Assigned

Organization's Unique Protocol ID:

HMC-QAD-F No. IREB-1221

Study Type:

Interventional Study (Randomized Controlled Trial)

Study Design:

Parallel Assignment, Open Label

Sponsor:

Hayatabad Medical Complex, Peshawar, Pakistan

Responsible Party:

Principal Investigator

Principal Investigator:

[name]

Principal Investigator

Department of Surgery

Hayatabad Medical Complex, Peshawar, Pakistan

Ethics Approval:

Approved by Ethical Committee, Hayatabad Medical Complex, Peshawar

Approval Number: HMC-QAD-F No. IREB-1221

Study Start Date:

01 August 2020

Primary Completion Date:

31 August 2025

Study Completion Date:

15 September 2025

Study Design: Open-label, parallel group, randomized controlled trial

Objective:

To compare postoperative complication rates between **onlay** and **sublay** mesh repair in adult patients with incisional hernia.

Study Population:

- **Inclusion Criteria:**

- Adults aged 18–60 years
- Primary incisional hernia
- Fit for open mesh repair
- Able to provide informed consent

- **Exclusion Criteria:**

- Obstructed/strangulated hernia
- Recurrent hernia
- BMI > 40
- ASA ≥ 3 or severe comorbidities
- Unable/unwilling to follow up

Sample Size: 350

Randomization:

- Randomized 1:1 to **onlay** or **sublay** repair
- Computer-generated random sequence

Interventions:

- **Experimental:** Sublay Mesh Repair — mesh placed in retromuscular/preperitoneal plane
- **Active Comparator:** Onlay Mesh Repair — mesh placed over anterior rectus sheath

Primary Outcome:

- Postoperative complication rate within 30 days (wound infection, seroma, hematoma, recurrence)

Secondary Outcomes:

- Hernia recurrence at 6 and 12 months
- Length of hospital stay
- Operative time

Follow-up:

- Clinical assessment on day 7, day 30, 6 months, and 12 months postoperatively

Ethics:

- Approved by Institutional Review Board, HMC (HMC-QAD-F No. IREB-1221)
- Written informed consent obtained from all participants

Data Management:

- Data recorded in secured database and standardized proforma
- Patient identifiers removed for any shared datasets.
- SPSS V23. Is used for data entry.

Statistical Analysis Plan (SAP)

Official Title:

Comparison of Complication Rates of Onlay vs Sublay Mesh Repair of Incisional Hernia

Brief Title:

Complication Rate of Onlay vs Sublay Mesh Repair in Incisional Hernia

ClinicalTrials.gov Identifier:

NCT ID: Not Yet Assigned

Organization's Unique Protocol ID:

HMC-QAD-F No. IREB-1221

Study Type:

Interventional Study (Randomized Controlled Trial)

Study Design:

Parallel Assignment, Open Label

Sponsor:

Hayatabad Medical Complex, Peshawar, Pakistan

Responsible Party:

Principal Investigator

Principal Investigator:

[name]

Principal Investigator

Department of Surgery

Hayatabad Medical Complex, Peshawar, Pakistan

Planned Statistical Analysis:

Comparative analysis of postoperative complication rates between onlay and sublay mesh repair techniques using appropriate descriptive and inferential statistical methods.

Ethics Approval:

Approved by Ethical Committee, Hayatabad Medical Complex, Peshawar

Approval Number: HMC-QAD-F No. IREB-1221

Analysis Population:

- All randomized patients
- Per-protocol population for sensitivity analysis

Descriptive Statistics:

- Continuous variables: mean \pm SD or median (IQR)
- Categorical variables: frequency (%)

Primary Outcome Analysis:

- Compare **postoperative complication rate** between onlay and sublay groups
- **Statistical Test:** Chi-square or Fisher's exact test
- Significance level: $\alpha = 0.05$

Secondary Outcome Analysis:

1. **Hernia recurrence:** Chi-square test; Kaplan-Meier curves for time-to-recurrence
2. **Length of hospital stay:** Independent t-test or Mann-Whitney U test
3. **Operative time:** Independent t-test or Mann-Whitney U test

Subgroup Analysis (optional):

- Stratified by age group (<40 vs \geq 40)
- Stratified by BMI (<30 vs 30–40)

Handling Missing Data:

- Multiple imputation if missing $>5\%$
- Sensitivity analysis comparing complete case vs imputed dataset

Software:

- Analysis performed using **SPSS version 23**

Reporting:

- Two-sided p-values
- 95% confidence intervals for effect estimates
- Tables and figures for primary and secondary outcomes

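### Optional, cheap improvement and not an error: the valid unadjusted primary test leaves baseline age and BMI unused, and the choice between chi-square and Fisher's test has no rule

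*SAP*

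**What the plan says.** The SAP's Primary Outcome Analysis names a "Chi-square or Fisher's exact test" at alpha 0.05. The Reporting section adds two-sided p-values and "95% confidence intervals for effect estimates", without naming the primary effect measure. No covariate-adjusted model is planned for any outcome.

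Age and BMI appear in three places:

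- **Protocol, Inclusion Criteria:** "Adults aged 18–60 years".
- **Protocol, Exclusion Criteria:** BMI above 40 is excluded.
- **SAP, Subgroup Analysis (optional):** "Stratified by age group", cut at 40 years, and "Stratified by BMI", cut at 30.

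On data, the protocol says only "Data recorded in secured database and standardized proforma" and lists no baseline variables. Missing data are handled by "Multiple imputation if missing" exceeds 5%, with no account of how the imputed sets feed the primary comparison. The software is "SPSS version 23". The protocol gives 350 patients randomised 1:1 with no stratification factors, an open-label design and primary completion on 31 August 2025.

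**The concern.** Two baseline variables that every screened patient must have are left out of the primary comparison. If they predict complications, adjusting for them narrows the confidence interval at the same sample size. If they do not, the price is a very small loss of precision.

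The word *or* in the test line leaves a second choice open. Fisher's test is conservative at this sample size, so the two tests differ in power and can fall on opposite sides of 0.05 for the same table. The analyst is given no rule for choosing between them.

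What is at stake is a few points of power and one avoidable analyst choice. The validity of the trial's conclusion is not at stake.

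**Working it through.** **Inputs from the documents.** 350 patients, 1:1, so 175 per arm; binary primary outcome; two-sided alpha 0.05; age 18 to 60; BMI at most 40.

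**Inputs assumed, because the documents give none.** Complication rates (onlay vs sublay) of 30% vs 18%, 25% vs 15% and 20% vs 10%; prognostic strength of age and BMI over a range; BMI normal (29, 5) truncated to 18–40; age uniform; no dropout in the power runs. The figure of 350 cannot be reproduced, since no power, rates or effect size is stated.

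**Step 1. Normal approximation at 25% vs 15%.** The difference is 0.10 and the pooled rate 0.20.

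- SE under no effect: √(0.20 × 0.80 × 2/175) = 0.04276
- SE under the alternative: √((0.25 × 0.75 + 0.15 × 0.85)/175) = 0.04243
- Power = Φ((0.10 − 1.96 × 0.04276)/0.04243) = Φ(0.38) = 64.9%

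If the covariates explain a share R² of outcome variance, both SEs shrink by √(1 − R²). At R² = 0.05 the factor is 0.9747, and power = Φ((0.10 − 1.96 × 0.04168)/0.04135) = Φ(0.44) = 67.1%, a gain of 2.2 points. At R² = 0.02 the gain is 0.9 points; at 0.10 it is 4.6.

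**Step 2. Exact power of the two named tests.** Every possible 2×2 table with 175 per arm was weighted by its binomial probability, and the weights of tables with p ≤ 0.05 were summed.

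| Onlay vs sublay | Chi-square | Fisher | Loss with Fisher |
|---|---|---|---|
| 30% vs 18% | 75.3% | 71.4% | 3.9 |
| 25% vs 15% | 65.4% | 60.3% | 5.1 |
| 20% vs 10% | 75.7% | 71.0% | 4.7 |

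At 20% in both arms the chi-square test's type I error is 5.05%.

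**Step 3. Simulated gain from adjustment.** 40,000 paired trials per scenario compared the Pearson chi-square with a logistic model on arm, BMI and age. The model was standardised to a risk difference with an influence-function SE. Odds ratios per SD (BMI/age) were 1.0/1.0, 1.3/1.2, 1.6/1.3 and 2.0/1.5. The table gives power points gained (paired simulation error at most 0.15).

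| Onlay vs sublay | None | Weak | Moderate | Strong |
|---|---|---|---|---|
| 30% vs 18% | 0.1 | 0.9 | 1.9 | 4.4 |
| 25% vs 15% | −0.2 | 0.5 | 1.6 | 3.6 |
| 20% vs 10% | −0.2 | 0.2 | 1.1 | 2.9 |

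The ratio of unadjusted to adjusted variance converts to patients as 350 × (ratio − 1):

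- None: 0.993–0.994, about 2 patients lost
- Weak: 1.007–1.014, 2 to 5 gained
- Moderate: 1.028–1.046, 10 to 16 gained
- Strong: 1.074–1.106, 26 to 37 gained

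The strong case corresponds to R² of about 7–10%.

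**Step 4. Checks on the adjusted analysis.** Its type I error at 20% vs 20% was 5.0–5.2%, and 95% CI coverage was 94.7–95.1%. None of the 640,000 fits failed to converge. With 10.2% of outcomes missing at random, 20 imputations and moderate covariates, coverage was 95.3% and type I error 4.7%.

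**Step 5. A stronger assumption.** A separate simulation (6,000 trials per scenario) with odds ratios per SD of 2.5 for BMI and 2.0 for age, R² about 0.16, gained 7.4 points at 25% vs 15% and 5.6 at 30% vs 17%. The strong column in Step 3 is therefore not a ceiling.

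**The case against.** The strongest reply is that this is reviewer preference. The planned test holds its size, the randomisation is not stated to be stratified, and no design feature calls for adjustment. Every figure for the gain rests on assumed rates and odds ratios, and the documents cannot show that any gain exists. A one-line test would become a standardised logistic model with Rubin's rules, and it has not been shown that the named software can run it. With an open-label trial and a primary completion date of 31 August 2025, outcomes by arm may already be known.

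Most of that stands. It is why the point is optional, why the size is given as a range, and why the fix has two branches. The reply does not remove two facts: eligibility requires both variables, and the test line offers two tests of different power without a rule. The second is worth more than weak or moderate adjustment and can be settled without new software.

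A reader might infer more: that the unadjusted test is biased or invalid, or that the missing rule shows an intention to pick the more favourable p-value. The documents support neither. Randomisation protects the unadjusted comparison, and an unstated rule is not evidence of how it would be used.

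**Conclusion.** The point holds as an optional, low-priority improvement. The planned primary analysis is valid. In all three assumed scenarios, the open choice between the two tests matters more (3.9 to 5.1 points) than weak or moderate adjustment (0.2 to 1.9 points). Strong covariates would add 2.9 to 4.4 points, and still stronger ones more. If age and BMI carry no information, adjustment costs under 1% of precision.

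It would be tempting to read the strong case as an upper limit, or as the gain to expect. Neither reading is supported, because the documents give no prognostic strength for either variable. All these sizes depend on the assumed event rates as well. The unnamed primary effect measure is a reporting detail settled by the same amendment, not a separate defect.

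**What to change.** **If outcomes by arm have not been examined,** replace the primary test line with text to this effect:

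> The primary analysis is a logistic regression of any complication within 30 days on arm, baseline BMI and baseline age (both continuous), standardised to a marginal risk difference (sublay minus onlay), with a robust (influence-function) standard error, 95% CI and two-sided p-value at alpha 0.05. If multiple imputation is used, the imputation model contains arm, BMI, age and the outcome, and Rubin's rules are applied to the risk difference and its variance. The single supportive test, and the primary test if the model does not converge, is the Pearson chi-square without continuity correction, with a Newcombe 95% CI for the risk difference. Fisher's exact test replaces it only if an expected cell count is below 5.

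The marginal risk difference keeps the target on the scale of the planned comparison and avoids moving to a conditional odds ratio. With 175 per arm, the expected number of events in each arm is half the total, so the Fisher rule applies only with fewer than 10 events overall (10/350 = 2.9%). The same holds, with events and non-events exchanged, for fewer than 10 non-events.

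**If outcomes by arm are already known,** keep the Pearson chi-square as primary, with the same Fisher rule and the Newcombe CI. Report the adjusted model as a labelled sensitivity analysis.

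**Cost.** A short SAP amendment; possibly software other than SPSS version 23 (the method ran in Python); under 1% loss of precision if age and BMI are not prognostic; and a check that the proforma holds both as continuous values, since no baseline data list is given. No new data collection is expected.

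### Must the SAP say which recurrence time point leads, and how patients lost before 12 months are counted?

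*SAP*

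**What the plan says.** - SAP, Secondary Outcome Analysis, item 1: "Chi-square test; Kaplan-Meier curves for time-to-recurrence". No time point, between-arm contrast for the curves or censoring rule is given.
- Protocol, Secondary Outcomes: "Hernia recurrence at 6 and 12 months". Follow-up: "Clinical assessment on day 7, day 30, 6 months, and 12 months postoperatively".
- SAP, Analysis Population: "All randomized patients", with a per-protocol set for sensitivity.
- SAP, Handling Missing Data: "Multiple imputation if missing" exceeds 5%, plus a comparison of complete-case and imputed results. The rule is general and not tied to any outcome.
- SAP, Reporting: "95% confidence intervals for effect estimates".

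The documents give no expected recurrence rate and no expected loss to follow-up.

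**The concern.** Item 1 of the SAP, read alone, leaves an analyst several choices: test at 6 months, at 12 months or at both; lead with the chi-square or the curves; and handle early leavers in more than one way. The trial is open-label and neither document ranks the two time points, so emphasis could be placed after the results are seen.

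The counting question looks more serious. With all randomized patients as the population, a patient last seen at 6 months could be handled in three ways:

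- **(a)** left out, so that only patients seen at 12 months are analysed;
- **(b)** kept if recurrence was already recorded, dropped if recurrence-free;
- **(c)** counted as recurrence-free.

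If loss is random, (a) is unbiased, (b) overstates the risk and (c) understates it. At stake are the reported recurrence risks and their difference and, if loss differs between arms, the 5% level of the test.

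**Working it through.** **Inputs.** From the protocol: 350 patients randomized 1:1, so 175 per arm. From the SAP: two-sided tests, with α = 0.05 stated for the primary outcome and taken to apply here. All else is assumed: 12-month risk p of 12% vs 5%; the share s of cumulative hazard falling by 6 months, 0.5 (constant) or 0.8 (early-weighted); random loss L after the 6-month visit. The plan has no recurrence figure to reproduce.

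**Step 1: time point.** The protocol defines the outcome at 6 and 12 months and the SAP analyses that outcome, so the natural reading is a chi-square at each. With no true difference, the two statistics have correlation √[p6(1−p12)/(p12(1−p6))]. For 5% and 10% this is √(0.045/0.095) = 0.688, and at least one test is significant in 8.4% of trials. For 5% and 6% it is √(0.047/0.057) = 0.908, giving 7.0%. Independent tests would give 1 − 0.95² = 9.75%. Naming a lead while still testing both leaves these figures as they are.

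With a true 12% vs 5%, the two tests disagree in 34% (constant) or 16% (early-weighted) of simulated trials. Much of that is power: 39% to 57% at 6 months against 66% at 12. The two risks are also different quantities.

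**Step 2: counting rules.**

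- Risk by 6 months: F6 = 1 − (1−p)^s
- Known recurrences: E = F6 + (1−L)(p − F6)
- Known recurrence-free: N = (1−L)(1−p)
- Rule (a): (1−L)p / [(1−L)p + (1−L)(1−p)] = p, unbiased
- Rule (b): E/(E+N)
- Rule (c): E

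For p = 0.12, s = 0.5, L = 0.20: F6 = 1 − √0.88 = 0.0619; E = 0.0619 + 0.8 × 0.0581 = 0.1084; N = 0.8 × 0.88 = 0.704. Rule (b) gives 0.1084/0.8124 = 0.1334.

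| Loss | Rule | Constant | Early-weighted | Error in the 7-point difference |
|---|---|---|---|---|
| 5% | (b) | 12.29% vs 5.13% | 12.45% vs 5.20% | +0.16 to +0.25 points |
| 20% | (b) | 13.34% vs 5.60% | 14.09% vs 5.95% | +0.74 to +1.14 points |
| 20% | (c) | 10.84% vs 4.51% | 11.54% vs 4.80% | −0.67 to −0.26 points |

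The standard deviation of the estimated difference at 20% loss (constant hazard) is 3.15 points. With equal 20% loss and a true 10% in both arms (constant hazard), rule (b) rejects in 5.0% of trials.

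**Step 3: the planned imputation.** In 20,000 simulated trials with 20 imputations, 20% loss and known recurrences kept:

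- with arm and 6-month status in the model: 12.1% vs 5.1%;
- with arm only: 13.4% to 14.2% vs 5.7% to 6.0%;
- Kaplan-Meier: 12.0% vs 5.0%.

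With 30% vs 10% loss and a true 10% in both arms, imputation with 6-month status rejects in 5.0% to 5.1% of trials. Without it the figure is 6.4% to 8.8%, and for rule (b) 6.6% to 9.3%.

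**Step 4: gain from a Kaplan-Meier contrast.** At 5% loss the standard error under (a) is 1.012 to 1.021 times that of Kaplan-Meier, a gain of 1% to 2%.

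**The case for a change.** The best argument for a change is that rule (b) can arise from ordinary coding. If the variable is recurrence by 12 months, a patient who recurred at 6 months has a known value while a recurrence-free leaver is missing. A complete-case analysis of that variable is then rule (b), and imputation by arm alone reproduces its bias. The SAP gives no imputation model, is silent at 5% missing or less, and could impute a patient for the chi-square whom the curves censor. A few sentences would close all of this.

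The mechanism is real, but its reach is small. At 5% missing or less, the error is at most about a quarter of a point. Above 5%, imputation applies, and 6-month status is a planned outcome and the obvious predictor of 12-month status, so leaving it out would be poor practice, not adherence to the plan. Rule (c) fits badly with a plan that treats absent status as missing. Imputing for one analysis and censoring in another is normal when the curves are descriptive.

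It is also true that no lead is named, and that the SAP offers Fisher's exact test for the primary outcome but not for recurrence. At 5% vs 2% with constant hazard, about 3.1 recurrences per arm would be expected at 6 months under the null (175 × (0.0253 + 0.0101)/2), too few for the usual chi-square rule. An analyst meeting sparse counts would use the exact test already listed. None of this makes the planned analysis wrong.

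**Conclusion.** No change follows. The protocol supplies the time points and the SAP's general rule covers missing status. The lead time point, the censoring rule and the contents of the imputation model are left unstated, which is a minor specification gap in a secondary outcome and does not touch the primary analysis. Followed sensibly, the plan gives unbiased or nearly unbiased risks under random loss: 12% vs 5% from patients seen at 12 months, 12.1% vs 5.1% from imputation using 6-month status. The distortions (up to 1.14 points at 20% loss, or rejection of up to 9.3% with 30% vs 10% loss) need a counting rule or an imputation model that neither document plans.

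These sizes rest on assumed recurrence rates, hazard shapes and random loss after 6 months. Loss related to recurrence would bias every method considered, Kaplan-Meier included, so it gives no reason to prefer different wording.
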